	APPENDIX 1: Description of database.....	23

PROTOCOL APPROVAL

Orphans Unite: chILD better together – European Management Platform for Childhood Interstitial Lung Diseases: chILD-EU database and observational study

Funding Reference Number : 305653

Signatures

[name]
Chief Investigator

Signature

Date

[name]
Trial Statistician

Signature

Date

[name]
Sponsor(s) Representative

Signature

Date

Principal Investigator

Signature

Date

LIST OF ABBREVIATIONS

ACCORD	Academic and Clinical Central Office for Research & Development - Joint office for University of Edinburgh and NHS Lothian
chILD	Childhood Interstitial Lung Disease
CRF	Case Report Form
CT	Computed Tomography
ECTU	Edinburgh Clinical Trials Unit
GCP	Good Clinical Practice
HR	Heart Rate
ILD	Interstitial Lung Disease
ISF	Investigator Site File
PEDS QL	Pediatric Quality of Life Inventory
QoL	Quality of Life
R&D	Research and Development
REC	Research Ethics Committee
RR	Respiratory Rate
SOP	Standard Operating Procedure
SpO2	Blood Oxygen Saturation

SUMMARY

This protocol describes two sequential interlinking studies required for the same population.

1. Establishment of a common European Database, with biobank and Peer Review confirmation of cases and annual review of progress and diagnosis
2. An observational study of treatment and outcomes in the first 12 months of diagnosis

1 INTRODUCTION

1.1 BACKGROUND

Paediatricians frequently see children with a respiratory rate as high as 80/min, perhaps with failure to thrive and hypoxemia. Within this non-specific clinical spectrum will be children with childhood interstitial lung diseases (chILD) (Deterding 2010). ChILD may also present dramatically in a term baby with severe unremitting respiratory distress leading to early death (Langston and Dishop 2009). These are rare diseases, frequently not diagnosed because the presentation is non-specific, and comprise a large number of disparate childhood specific entities as well as the spectrum known from adult ILD (Fan and Langston 2002). Even if the possibility of chILD is considered, there is no standard diagnostic pathway, prognosis is unknown, and treatment is anecdotal, despite the discovery of a few molecular causes (for example, mutations in surfactant protein genes) (Doan, Guilleman et al. 2008).

Progress is very slow because of (a) lack of diagnostic awareness; (b) rarity of chILD (< 1:50-100,000 children, 1-2 orders of magnitude less than adult ILD); (c) large number of individual conditions (>200) that occur under the chILD umbrella; (d) unfamiliarity with the diseases and lack of established diagnostic pathways; (e) lack of resources for complex collaborations to assemble cohorts in which scattered, but well defined entities are followed; and (f) lack of standardized and quantifiable outcomes to enable controlled observations for any evidence based guidelines (Dishop 2011).

Our overarching study (ChILD-EU Orphans Unite), funded by an FP7 grant, will bring leading European clinical scientists and paediatric pulmonologists with expertise in chILD into collaboration in order to (a) increase diagnostic awareness and tie together all chILD across Europe; (b) ensure these patients are characterised in a uniform manner, with expert verification of diagnoses by international panels of clinicians, radiologists, geneticists and pathologists; (c) establish a pan-European database and bio-bank compatible with others worldwide; (d) assess currently used treatments; (e) refine relevant clinical outcomes; (f) perform quality controlled observations of all interventions; (g) run the first randomised and controlled interventions of off-label treatments in chILD, and (h) prepare and implement evidence-based guidelines and treatment protocols for chILD in Europe.

This protocol is in two parts

- (A) to describe the European ChILD-EU database and data collection
- (B) to outline objective (f) of the overarching study; a controlled observational study of interventions used to assess and treat infants and children with chILD.

The protocol is combined in two parts as whilst the plans are integrated it is anticipated that Part A will continue longer term once Part B is complete.

1.2 RATIONALE FOR STUDY

There are limited studies bringing together children with interstitial lung disease and no studies assessing the response to standardised interventions in ChILD. The paucity of cases in each centre and the lack of evidence based treatment approach require a structured observation of current practice to inform future research direction. We aim to capture interventions and outcomes in well-characterised patients with suspected and proven ChILD. Such information will provide data on outcome in relation to standard interventions and support further research directions.

Part A: ChILD-EU Database and Biobank

The objective of the ChILD-EU Database and biobank is to build a descriptive collection of children with interstitial lung disease together with core biobank materials. The minimum dataset will include demographics, disease descriptors, investigations and the conclusions of an international peer review diagnostic team (www.childeu.net). Each case will be reviewed on an annual basis to ensure diagnostic accuracy and data entered from clinical encounters

into the database. The biobank will include as a minimum a blood sample for genetic analysis, digital radiology imaging, and digital imaging of pathology samples from lung biopsy where possible.

Part B: ChILD-EU Observational Study

The observational study aims to provide detailed information about outcomes and responses to treatment in the first year of diagnosis. We intend to study children more intensely through this period to better understand the burden of disease, outcomes and responses to standard investigations that may lead to further study.

2 STUDY OBJECTIVES

2.1 OBJECTIVES

Part A: ChILD-EU Database and Biobank

2.1.1 Primary Objective

To collate detailed information on clinical cases of possible ChILD on a central database and biobank.

2.1.2 Secondary Objectives

- (a) To review each case by an experienced international interdisciplinary peer review team to provide diagnostic oversight and feedback
- (b) To provide annual updates of diagnosis and outcome in a feedback loop via peer review
- (c) To store for future research, blood samples for genetic analysis of cases and parents
- (d) To support paediatricians and families caring for children with ChILD

Part B: ChILD-EU Observational Study

2.1.3 Primary Objective

To describe outcomes at 1, 2, 3, 6 and 12 months in infants and children with ChILD.

Outcomes measured will be

- death,
- survival on artificial ventilatory support (invasive or non-invasive),
- survival in supplemental oxygen,
- survival breathing room air,
- quality of life (QoL)

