2.1.4 Secondary Objectives

To describe variance in outcome at 1, 2, 3, 6 and 12 months in infants and children with ChILD according to

1. Diagnosis and Presentation
 - a. Diagnosis (Peer Review)
 - b. Diagnostic certainty (Peer Review)
 - c. Computed Tomography (CT) score – by component radiologist (Peer review)
 - d. Blood Oxygen Saturation (SpO₂) at rest in room air at presentation
 - e. SpO₂ asleep in room air at presentation (nadir)
 - f. Respiratory Rate (RR) (z score) at rest in air at presentation
 - g. Heart rate (HR) (z score) in air at presentation

- h. Blood pressure at rest for 5 minutes at presentation
 - i. Weight (z-score) at presentation
 - j. Leland Fan 5 point severity score (Nil, symptoms, SpO₂ <90% air asleep, SpO₂ at rest, Pulmonary Hypertension).
 2. Time to treatment and improvement
 - a. Time from onset of symptoms/signs of ChILD to first treatment
 - b. Time from onset of symptoms/signs of ChILD to diagnosis (local clinical)
 - c. Time from onset of symptoms/signs of ChILD to normoxia whilst awake (SpO₂ ≥94% breathing room air at rest)
 - d. Time from onset of symptoms/signs of ChILD to respiratory rate in normal range for age (Fleming, Thompson et al. 2011)
 - e. Time from onset of first treatment to reduction in RR by 10%
 - f. Time from onset of first treatment to reduction in HR by 20%
 - g. Time from onset of symptoms/signs of ChILD to normoxia whilst asleep (SpO₂ ≥94% breathing room air at rest)
 - h. Time from onset of symptoms/signs of ChILD to weight appropriate for age/height without use of calorie supplementation
 - i. Time from onset of treatment to improvement in weight by 10%
3. Treatments
 - a. Steroids
 - i. Use of steroids
 - ii. Dose, route and frequency of steroid use
 - iii. Time from first presentation to initiation of steroids
 - iv. Number of concomitant ChILD treatments at time of starting steroids
 - b. Hydroxychloroquine
 - i. Use of Hydroxychloroquine
 - ii. Dose and frequency of hydroxychloroquine
 - iii. Time from first presentation to initiation of hydroxychloroquine.
 - iv. Number of concomitant ChILD treatments at time of starting hydroxychloroquine
 - c. Azithromycin
 - i. Use of Azithromycin
 - ii. Dose and frequency of Azithromycin
 - iii. Time from first presentation to initiation of Azithromycin.
 - iv. Number of concomitant ChILD treatments at time of starting Azithromycin
4. Concomitant Medicines
5. Follow up Review
 - a. SpO₂ in room air measured 4 weeks after commencing initial treatment

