2.2.1 Primary Endpoint

12-month review or time to death.

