4 STUDY POPULATION

4.1 NUMBER OF PARTICIPANTS

Part A: ChILD-EU Database and Biobank

The number of participants is limited by patient presentation only. The study is open to presentation from all European countries, but has focussed support in France, Germany, Italy, Turkey and the United Kingdom. In the UK and Ireland prevalence was estimated as 3.6 per million children, but is likely under-estimated due to misdiagnosis and the absence of a common register.

The number of sites will be determined in each contributing country.

Part B: ChILD-EU Observational Study

We anticipate that there will be approximately 130 patients per year across Europe who may be eligible. As the population has a high degree of diagnostic uncertainty, few treatment options and the study does not require significant additional investigations, we anticipate a high recruitment level from this number. We would hope to continue recruitment for 30 months.

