8.2 PROPOSED ANALYSES

Part A: ChILD-EU Database and Biobank

There will be descriptive statistics of cases and outcomes only.

Part B: ChILD-EU Observational Study

Analysis [1st 12 months]

Initial analysis will be descriptive presenting changes over time in characteristics measured broken down by key variables of interest such as type of treatment, diagnosis etc. To determine what factors are related to outcome we will model outcome with collected data taking into account likely covariates. If appropriate we will consider missing data using the guidelines from www.missingdata.org.uk.

Analysis [2nd 12 months]

Repeat of the same type of analysis as for 1st period. Possibly with addition of comparisons of response rates between two periods

The study will have a statistical analysis plan containing full details of the statistical aspects of this study produced by the trial statistician prior to seeing the data.

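### The Part B outcome states do not mention lung transplantation, so a recipient alive without respiratory support cannot be told apart from a child whose own lungs recovered

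*Protocol*

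**What the plan says.** The primary objective of Part B (Protocol 2.1.3) is "To describe outcomes at 1, 2, 3, 6 and 12 months in infants and children with ChILD". The outcomes listed under it are death, survival on ventilatory support of either kind, "survival in supplemental oxygen", "survival breathing room air", and quality of life. The primary endpoint (2.2.1) is "12-month review or time to death".

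Section 2.1.4 describes how outcome varies with diagnosis, severity at presentation and drug treatment. It also lists time-to-improvement measures, such as "Time from onset of symptoms/signs of ChILD to normoxia whilst awake" (item 2c), with a parallel measure for normoxia asleep (2g) and one for a normal respiratory rate (2d). Section 8.2 adds: "To determine what factors are related to outcome we will model outcome with collected data taking into account likely covariates".

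Transplantation does not appear in the outcomes, the named treatments, the improvement measures, the endpoint, the visit schedule (section 3), the withdrawal rules (5.5) or the analysis section (8.2).

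**The concern.** The three alive states record what support a child needs at a visit. They do not ask whether the child still has the lungs in which the disease was diagnosed. Severe disease is within scope: section 1.1 describes presentations that lead to early death, ventilated survival is an outcome state, and pulmonary hypertension is the last item of the severity score in 2.1.4. If such a child receives a transplant and later needs no support, the listed states place that child with those who recovered.

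The outcome is then broken down by diagnosis and treatment and modelled. A child who did not respond to drug treatment and was transplanted could enter those analyses as a drug-exposed child surviving in room air, and could also supply a time to normoxia. Any such distortion is in the favourable direction. It would fall on severe diagnoses, where numbers are small and where the protocol itself says prognosis is unknown.

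**Working it through.** The protocol states no figure on this point, so there is none to reproduce. The check is a reading of the outcome states followed by a bounding calculation.

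**Step 1: where a recipient falls under 2.1.3 at a given visit**

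| Status of the recipient at the visit | State under 2.1.3 | Confused with recovery? |
|---|---|---|
| Died | Death | No |
| Alive, ventilated | Survival on ventilatory support | No |
| Alive, on oxygen | Survival in supplemental oxygen | No |
| Alive, no support | Survival breathing room air | Yes |

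Only the last row is affected. The same child can satisfy items 2c, 2d and 2g of section 2.1.4, because none of them carries a transplant-free condition. Under 2.2.1 transplantation is neither an event nor a censoring point.

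**Step 2: inputs for size**

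- Accrual: "approximately 130 patients per year across Europe who may be eligible" (4.1).
- Recruitment period: 30 months hoped for (4.1), which is 2.5 years.
- Ceiling on numbers: 130 × 2.5 = 325. It is a ceiling because 130 counts children who may be eligible, not those recruited.
- Share transplanted within 12 months, *p*: not in the protocol. Assumed 0% to 5%.
- Share of recipients alive and off support at 12 months, *q*: not in the protocol. Set to 1 for the upper bound.

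**Step 3: bound**

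Children affected = 325 × *p* × *q*. Overstatement of the room-air share = *p* × *q*.

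| *p* (assumed) | Children affected, *q* = 1 | Overstatement |
|---|---|---|
| 0% | 0 | 0 points |
| 1% | 325 × 0.01 = 3.25, about 3 | about 1 point |
| 5% | 325 × 0.05 = 16.25, about 16 | about 5 points |

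If 60% of children were recorded in room air (an assumed 195 of 325), the share in room air without a transplant would be 192/325 = 59.1% with 3 recipients, or 179/325 = 55.1% with 16. Any *q* below 1 shrinks these differences in proportion.

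**Step 4: subgroups**

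One affected child in a subgroup of size *m* moves its room-air share by 100/*m* percentage points. In an illustrative subgroup of 20 that is 5 points per child. Section 1.1 puts more than 200 conditions under the chILD umbrella. Even 325 children spread evenly over 200 would give 325/200 ≈ 1.6 per condition, so diagnostic subgroups will often be small. Whether recipients cluster in any of them cannot be judged from the protocol.

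**The case against.** The strongest reply is that this is an omission, not an error. Section 2.1.3 sets out to describe the status of children with chILD. A description by support needed, whatever procedures have taken place, is a legitimate choice, and each label stays factually true for each child. A transplant may also be captured already: the section 3 table has generic outcome and treatment rows at all five follow-up visits, section 2.1.4 collects use of inpatient care, section 7 draws on hospital records, and section 13.2 has procedures outside the protocol's recommendations recorded. The CRF is not shown, and section 8.2 leaves statistical detail to an SAP that is also not shown.

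Much of this stands, and it rules out several stronger readings that a reader might infer:

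- *Every transplanted child is counted as a success.* The protocol has no such rule. Recipients who are ventilated, on oxygen or dead fall in other states.
- *Room air is the best state and transplantation a failure that goes unreported.* The protocol does not rank the states or define failure. The ordering is a reasonable inference, but not a stated rule.
- *Mortality is understated.* It is not. Deaths are counted as deaths. A combined rate of death or transplantation would be a different quantity, which the protocol does not claim to report.
- *The effect is known to be large.* The protocol gives no transplant rate, and the effect may be nil.

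The reply does not remove the point. The categories and the endpoint are set in the protocol, and an SAP can separate recipients only if the event and its date have been recorded. The generic rows and other records might hold the event, but nothing requires a date or links it to the outcome state. Part B also aims to describe responses to treatment (section 1.2), and a state that merges organ replacement with recovery serves that aim poorly.

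**Conclusion.** The point holds in limited form. Applied as listed, the states in 2.1.3 class a transplant recipient who is alive and off support with children whose own lungs recovered, and the normoxia and respiratory-rate measures in 2.1.4 can do the same. The size cannot be established from the protocol. The bound of about 0–5 percentage points on the overall room-air share (0–16 of at most 325 children) rests on an assumed transplant share of 0–5% and on every recipient being off support at 12 months. Small severe subgroups could be affected more. The change is worth making because it is cheap and because the event is easier to record as it happens than to recover later from many sites.

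**What to change.** - Record lung transplantation and its date on the CRF, unless the CRF already does so.
- In 2.1.3, add a separate state for children alive after lung transplantation, reported at 1, 2, 3, 6 and 12 months.
- In 2.2.1, report transplant-free survival alongside time to death.
- In 2.1.4, report SpO2 and respiratory rate measured after transplantation separately from the time-to-improvement measures.

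The cost is at most one CRF item with a date, plus short edits to the outcome and endpoint sections. No visits or patients are added and clinical care is unchanged. The reported room-air share may become slightly smaller.

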2.1.4 Secondary Objectives

To describe variance in outcome at 1, 2, 3, 6 and 12 months in infants and children with ChILD according to

1. Diagnosis and Presentation
 - a. Diagnosis (Peer Review)
 - b. Diagnostic certainty (Peer Review)
 - c. Computed Tomography (CT) score – by component radiologist (Peer review)
 - d. Blood Oxygen Saturation (SpO₂) at rest in room air at presentation
 - e. SpO₂ asleep in room air at presentation (nadir)
 - f. Respiratory Rate (RR) (z score) at rest in air at presentation
 - g. Heart rate (HR) (z score) in air at presentation

- h. Blood pressure at rest for 5 minutes at presentation
 - i. Weight (z-score) at presentation
 - j. Leland Fan 5 point severity score (Nil, symptoms, SpO₂ <90% air asleep, SpO₂ at rest, Pulmonary Hypertension).
 2. Time to treatment and improvement
 - a. Time from onset of symptoms/signs of ChILD to first treatment
 - b. Time from onset of symptoms/signs of ChILD to diagnosis (local clinical)
 - c. Time from onset of symptoms/signs of ChILD to normoxia whilst awake (SpO₂ ≥94% breathing room air at rest)
 - d. Time from onset of symptoms/signs of ChILD to respiratory rate in normal range for age (Fleming, Thompson et al. 2011)
 - e. Time from onset of first treatment to reduction in RR by 10%
 - f. Time from onset of first treatment to reduction in HR by 20%
 - g. Time from onset of symptoms/signs of ChILD to normoxia whilst asleep (SpO₂ ≥94% breathing room air at rest)
 - h. Time from onset of symptoms/signs of ChILD to weight appropriate for age/height without use of calorie supplementation
 - i. Time from onset of treatment to improvement in weight by 10%
3. Treatments
 - a. Steroids
 - i. Use of steroids
 - ii. Dose, route and frequency of steroid use
 - iii. Time from first presentation to initiation of steroids
 - iv. Number of concomitant ChILD treatments at time of starting steroids
 - b. Hydroxychloroquine
 - i. Use of Hydroxychloroquine
 - ii. Dose and frequency of hydroxychloroquine
 - iii. Time from first presentation to initiation of hydroxychloroquine.
 - iv. Number of concomitant ChILD treatments at time of starting hydroxychloroquine
 - c. Azithromycin
 - i. Use of Azithromycin
 - ii. Dose and frequency of Azithromycin
 - iii. Time from first presentation to initiation of Azithromycin.
 - iv. Number of concomitant ChILD treatments at time of starting Azithromycin
4. Concomitant Medicines
5. Follow up Review
 - a. SpO₂ in room air measured 4 weeks after commencing initial treatment
 - b. RR at rest measured 4 weeks after commencing initial treatment
 - c. Heart rate at rest measured 4 weeks after commencing initial treatment

6. Quality of Life score - PEDS QL Generic Core Scales
 - a. At 0 and 12 months.
7. Questionnaire for health care utilisation and costs
 - a. utilisation of inpatient and outpatient care to calculate direct costs gathered at 0, 3, 6 and 12 months
 - b. loss of productivity of parents and children to calculate indirect costs gathered at 0, 3, 6 and 12 months

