2.2.2 Secondary Endpoints

Described in section 2.1.4

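### Section 2.1.4 uses variables that arise after, or overlap with, the 1- to 12-month outcomes as factors for describing those outcomes, and 2.2.2 also calls them endpoints

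*Protocol*

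**What the plan says.** Section 2.1.3 defines the Part B outcomes as death, survival on ventilatory support, survival in supplemental oxygen, "survival breathing room air", and quality of life, at 1, 2, 3, 6 and 12 months.

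Section 2.1.4 opens with "To describe variance in outcome at 1, 2, 3, 6 and 12 months in infants and children with ChILD according to" and puts seven numbered groups under that one sentence. They include:

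- presentation and Peer Review findings (item 1);
- times to treatment, diagnosis and recovery (item 2), for example "Time from onset of symptoms/signs of ChILD to normoxia whilst awake";
- treatments and concomitant medicines (items 3 and 4);
- vital signs after treatment (item 5), for example "Heart rate at rest measured 4 weeks after commencing initial treatment";
- "Quality of Life score - PEDS QL Generic Core Scales" at 0 and 12 months (item 6);
- direct and indirect costs at 0, 3, 6 and 12 months (item 7).

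Section 2.2.2 gives the secondary endpoints in full as "Described in section 2.1.4". Section 8.2 begins with description by key variables. It then proposes to model outcome on the data collected, allowing for covariates, in order to find related factors. It defers full statistical detail to a SAP that is not at hand.

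**The concern.** The lead sentence gives every item the role of a factor by which outcome is broken down, while 2.2.2 gives the same items the role of endpoint. For items fixed at presentation, the factor role is sound. For items that arise during follow-up, it reverses or blurs the time order: 12-month quality of life cannot account for a death at 1 month, and at 12 months it is the outcome.

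Recovery times bring a further problem. A child must survive long enough to reach the event, so children with a recorded recovery time look protected from death even if recovery and death are unrelated (guarantee-time bias). This affects a plain descriptive table as much as a regression. Section 1.2 wants the study to inform later research in a rare disease, so an artefact presented as a correlate of outcome could mislead that work.

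**Working it through.** The protocol states no event rates, power or sample size calculation, so there is no figure to reproduce. Three checks follow.

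**1. Items against outcomes (2.1.4 against 2.1.3)**

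| Item | When it is known | Relation to the outcomes |
|---|---|---|
| 2c, 2g normoxia in room air, awake or asleep | when reached; clock runs from symptom onset | overlaps with room-air and oxygen states; unreachable after early death |
| 2d–2f, 2h, 2i respiratory rate, heart rate, weight | when reached; clock runs from symptom onset or treatment | not outcome states; unreachable after early death |
| 5 vital signs | 4 weeks after treatment start | about the same time as the 1-month outcome; before the later ones |
| 6 quality of life | 0 and 12 months | 0 months precedes all outcomes; 12 months is itself an outcome |
| 7 costs | 0, 3, 6, 12 months | 0 months precedes all; the others precede only some or none |

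**2. Count for the dated items (groups 5 to 7)**

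The five outcome times are 1, 2, 3, 6 and 12 months. Four weeks is taken as the 1-month visit. This is approximate, because item 5 counts from treatment start and section 3 starts participation at consent.

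| Item | Pairs | Before | Same time | After |
|---|---|---|---|---|
| Three 4-week vital signs | 15 | 12 | 3 | 0 |
| Quality of life, 0 months | 5 | 5 | 0 | 0 |
| Quality of life, 12 months | 5 | 0 | 1 | 4 |
| Two cost types, 0 months | 10 | 10 | 0 | 0 |
| Two cost types, 3 months | 10 | 4 | 2 | 4 |
| Two cost types, 6 months | 10 | 2 | 2 | 6 |
| Two cost types, 12 months | 10 | 0 | 2 | 8 |
| **Total** | **65** | **33** | **10** | **22** |

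All 22 pairs in the wrong order come from 12-month quality of life and follow-up costs. Those items make 5 + 30 = 35 pairs, of which only 6 have the item before the outcome.

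**3. Direction of the bias for recovery times and death**

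Assume death and recovery are unrelated, each with a constant rate. The protocol gives neither rate. Take a 12-month death risk of 10% and a 12-month recovery probability of 60%.

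- Monthly death rate: −ln(0.90)/12 = 0.00878. Monthly recovery rate: −ln(0.40)/12 = 0.0764.
- Neither event by 12 months: 0.90 × 0.40 = 0.36, so some event occurs with probability 0.64.
- Death before recovery: 0.00878/(0.00878 + 0.0764) × 0.64 = 0.066. Recovery first: 0.64 − 0.066 = 0.574.
- Death after recovery: 0.100 − 0.066 = 0.034.
- Death risk if recovery was recorded: 0.034/0.574 = 5.9%. If not: 0.066/0.426 = 15.5%.

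The true difference is nil. A simulation with n = 325 (130 a year × 2.5 years, the most the protocol's recruitment figures allow) and 2,000 runs per setting gave the same two risks. A two-sided 5% test was significant in 82% of runs. Over assumed death risks of 5% to 20% and recovery of 40% to 80%, the false-positive rate ran from 31% (2.8% against 6.4% dead) to nearly 100% (13.3% against 39.0%).

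With a landmark at 1 month (children alive then, grouped by recovery up to then, followed for later death), the expected risk in both groups is 1 − 0.90^(11/12) = 9.2%. The simulation gave 9.0% and 9.3%, and false-positive rates of 3% to 5% in all nine settings.

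**The case against.** The strongest reply is that the objective is only to describe, that 8.2 starts with description, and that its modelling sentence neither cites 2.1.4 nor makes every item a covariate. Covariate choice, landmarks and censoring normally belong in the SAP. On this view 2.1.4 is two lists run together under a loose lead-in, and 2.2.2 shows that the recovery and follow-up items were meant as endpoints.

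Much of this is plausible, and a drafting merger may well be the cause. It does not dispose of the point. The roles of factor and endpoint are assigned in the protocol and conflict there, and a SAP that follows both sections faithfully inherits the conflict. Description is no protection either, since step 3 is a simple two-group table.

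The objection does rule out several stronger readings:

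- **That all of items 5 to 7 come too late.** The 4-week vital signs generally precede the 2- to 12-month outcomes, 0-month quality of life and costs precede every outcome, and 3- and 6-month costs precede some. In 33 of 65 pairs the order is right.
- **That normoxia is the same event as surviving in room air.** Item 2c has a saturation threshold of 94%; the outcome is support status with no threshold. A child may breathe room air below 94%, or reach 94% and later need oxygen. They overlap strongly but are not identical.
- **That the other recovery times restate the outcome.** Respiratory rate, heart rate and weight are not outcome states. Their problem is timing and survival.
- **That artefacts will be reported as determinants of outcome.** Without the SAP this cannot be known.

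**Conclusion.** The point holds in limited form. Section 2.1.4 makes explanatory factors of 12-month quality of life, follow-up costs relative to earlier outcomes, times to normoxia in room air, and the other recovery times. Section 2.2.2 makes the same items endpoints, and 8.2 sets no time order. Followed as written, some associations would arise partly by construction. The description of outcomes under 2.1.3 is unaffected.

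The count in step 2 follows from the protocol's own schedule, given the reading of 4 weeks as 1 month. The percentages in step 3 rest on assumed rates, independence of death and recovery, and a split into recovered and not recovered that the protocol does not specify. They show direction and should not be read as the expected bias in this study. A reader might also model room-air status directly on normoxia and find near-perfect separation, but that result is built in once the two are equated, so it carries no weight here.

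**What to change.** Split section 2.1.4 into two lists.

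- **(A) Explanatory factors:** presentation and Peer Review items (item 1), 2a and 2b, treatments and concomitant medicines (items 3 and 4), and 0-month quality of life and costs.
- **(B) Secondary endpoints:** 2c to 2i, the 4-week vital signs (item 5), 12-month quality of life, and follow-up costs.

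Point section 2.2.2 to list (B) only.

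Add one sentence to section 8.2: a variable determined after entry may be related only to outcomes later than its measurement, either by a landmark analysis in children alive at that time or as a time-dependent covariate. This should expressly cover treatment started in follow-up, 4-week vital signs, recovery status, and 3- and 6-month costs. It keeps treatment response, which section 1.2 sets out to study, within the analysis. It also governs the Peer Review items, because sections 3 and 13.2 place Peer Review after consent, so they are not strictly fixed at entry.

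The cost is a re-ordering of one section and two short edits, with no new data. The downside is a little more analysis work and fewer children in each landmark analysis.
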